1.3 Schema

The general study design is summarised in Figure 1.

Figure 1 Study Design

bid = twice per day; BSC = best supportive care (for COVID-19 symptoms); SARS-CoV-2+ = severe acute respiratory syndrome coronavirus 2 positive.

2. INTRODUCTION

2.1 Background and Study Rationale

Coronavirus disease 2019 (COVID-19) is a new pandemic disease caused by the severe acute respiratory syndrome coronavirus 2 (SARS-CoV-2). In a retrospective study of 191 patients with COVID-19, sepsis was the most frequently observed complication, followed by respiratory failure, acute respiratory distress syndrome (ARDS), heart failure, and septic shock. While sepsis might be directly caused by SARS-CoV-2 infection, further research is needed to investigate the pathogenesis of COVID-19 illness. Most COVID-19 cases (~80%) are mild respiratory illnesses. 5% to 15% of these respiratory illnesses require hospitalization (mostly due to pneumonia) and can progress quickly to severe acute lung injury and ARDS (Huang et al 2020, Wu and McGoogan 2020, Zhou et al 2020), which is associated with high mortality.

Normally, human coronaviruses are detected and cleared by the immune system, but a subset of patients experience increased severity of symptoms (Channappanavar and Perlman 2017, Zhou et al 2020). These symptoms have been associated with the loss of control of the virally induced immune response (Li et al 2020). In these cases, the inflammatory response is hypothesized to be a major pathogenic mechanism of ARDS through modulation of pulmonary macrophages and dendritic cells (Channappanavar et al 2016, Huang et al 2005, Wong et al 2004, Yoshikawa et al 2009) and/or neutrophils (Herold et al 2015). Putative inflammatory mediators include interleukin (IL)-1 β , IL-6, IL-8, IL-10, tumor necrosis factor alpha (TNF α), and monocyte chemoattractant protein-1 (MCP-1) (Chen et al 2020, Herold et al 2015, Yoshikawa et al 2009). During the acute phase of coronavirus infection, T cells are the critical mediators of clearance of infection, while B cells generate a protective humoral response (Zhao et al 2009, Zhao et al 2014). Generation of antibodies against coronaviruses is not always protective. In a mouse model, an anti-spike immunoglobulins (specific to SARS-COV) could skew the inflammation-resolving response which lead to severe acute lung injury in mice (Liu et al 2019).

Bruton's tyrosine kinase (Btk) is a Tec family nonreceptor protein kinase, expressed in B cells, myeloid cells, osteoclasts, mast cells, and platelets. The function of Btk in signaling pathways activated by the engagement of the B-cell receptor has been well established (Buggy and Elias 2012). Btk is also involved in the following biologic processes: Fc gamma receptor signaling in myeloid cells, mast cell degranulation, and signaling through Toll-like receptors (TLRs) in macrophages and neutrophils. Specifically, Btk is required for TLR 7/8 signaling, which recognize single strand RNA viruses such as coronaviruses, signal through Btk in macrophages (Page et al 2018).

Recently, Btk inhibition has shown to rescue mice from lethal influenza A-virus induced acute lung injury by significantly decreasing lung inflammation and macrophage/monocyte mediated cytokines/chemokines (TNFa, IL-1β, IL-6, MCP-1, etc) in the lung homogenates. These results suggest that Btk inhibition may represent a new immunomodulatory treatment for virally induced lung damage driven by excessive inflammation (Florence et al 2018). Additionally, in a murine model of sepsis, acalabrutinib has shown to ameliorate the cardiac dysfunction by suppressing pro-inflammatory cytokines/chemokines associated with sepsis (O'Riordan et al 2019). Patients with hematologic malignancies treated with acalabrutinib (Calquence®) have shown significant reduction of several cytokines/chemokines including pro-inflammatory markers such as: TNFa (p<0.001), IL-10 (p<0.001), MCP-1 (p<0.01), MIP-1β (p<0.001), MIP-1α (p<0.001), IL-16 (p<0.001), TARC (p<0.001), CXCL13 (p<0.001), Granzyme A (p<0.001) (Byrd et al 2016, Covey 2017), and IL-6 (p<0.05) (data on file). Several of these cytokines/chemokines have been shown to be associated with more severe illness in COVID-19 patients. We hypothesize that acalabrutinib treatment will inhibit cells that produce pro-inflammatory cytokines/chemokines, will lead to reduced inflammation of the lungs in patients with COVID-19, and mitigate the pathophysiologic response that leads to the most severe morbidity and mortality associated with viral infection. Recently, encouraging results were reported in a case series of patients hospitalized with severe COVID-19 and treated with acalabrutinib led by investigators at the National Institutes of Health (Roschewski 2020). Similarly, other BTK inhibitors have shown promise in COVID-19 patients with hematologic malignancies (Thibaud et al 2020, Treon et al 2020).

Together, strong scientific evidence justifies a clinical trial in this patient population. The purpose of this study is to evaluate the safety and preliminary efficacy of adding acalabrutinib to best supportive care (BSC) for subjects hospitalized due to COVID-19 symptoms.

2.2 Benefit/Risk Assessment

The lack of established treatments and vaccines for the novel SARS-CoV-2 virus has driven major medical centers to an unprecedented overload, which has undoubtedly contributed to the mortality observed with this disease. While vaccines and antiviral therapies are urgently needed, drugs that can address the pathophysiology of the disease to decrease the morbidity and mortality and reduce hospital admissions and intensive care unit (ICU) use are also needed without delay.

Btk inhibition may serve as an important addition to the COVID-19 armamentarium by reducing the viral-induced hyperimmune response, which leads to lung destruction. Acalabrutinib is currently approved in the United States for the treatment of patients with mantle cell lymphoma or chronic lymphocytic leukemia/small lymphocytic lymphoma. As of 30Oct2019, acalabrutinib has been administered to over 3300 participants in clinical studies, including subjects with hematologic malignancies, solid tumors, or rheumatoid arthritis, and participants who are healthy subjects or those with mild to moderate hepatic impairment. No

serious adverse events (SAEs) have been reported in the hepatic impairment trial or in the healthy volunteer trials. Some subjects with chronic lymphocytic leukemia have been receiving acalabrutinib therapy for more than 5 years. Acalabrutinib has been administered alone and in combination with other kinase inhibitors, anti-CD20 antibodies, chemoimmunotherapy (eg, bendamustine/rituximab), and an anti-programmed cell death 1 (PD-1) receptor antibody. No dose-limiting toxicities (DLTs) have been identified for acalabrutinib monotherapy or when administered in combination with the aforementioned agents. Current clinical safety data supports combining acalabrutinib with other agents.

Refer to the acalabrutinib Investigator's Brochure for the most up to date safety and efficacy information. Identified risks for acalabrutinib are summarized in Section 6.6 and are based on events observed in subjects with cancer who have been on long-term treatment with acalabrutinib 100 mg twice daily (bid).

Based on the safety profile of acalabrutinib to date, no overt toxicities have been identified that would preclude acute treatment for subjects with moderate to severe COVID-19 symptoms.

Precautionary safety measures, in addition to regular monitoring of safety by an internal Data Monitoring Committee (iDMC) and the Sponsor, are included in the study design to enable early identification of safety signals in the study and minimize the risk to subjects.

3. OBJECTIVES AND ENDPOINTS

Pr	imary Objectives	Primary Endpoints/Variables
•	To evaluate the safety of acalabrutinib in subjects with COVID-19 when administered with BSC	 Safety Type, frequency, severity, and relationship to study treatment of any TEAEs or
•	To evaluate the efficacy of adding acalabrutinib to BSC for the treatment of COVID-19	abnormalities of laboratory tests, SAEs, or AEs leading to discontinuation of study treatment. Efficacy
		 Proportion of subjects alive and free of respiratory failure at Day 28
		 For the purpose of this study, respiratory failure, is defined based on resource utilization of any of the following modalities: (a) Endotracheal intubation and mechanical ventilation
		(b) Oxygen delivered by high-flow nasal cannula (heated, humidified, oxygen

Table 3Protocol Objectives and Endpoints

	 delivered via reinforced nasal cannula at flow rates >20 L/min with fraction of delivered oxygen ≥0.5) (c) Noninvasive positive pressure ventilation or continuous positive airway pressure (d) Extracorporeal membrane oxygenation
Secondary Efficacy Objective	Secondary Efficacy Endpoints/Variables:
To evaluate the efficacy of adding acalabrutinib to BSC for the treatment of COVID-19	 Proportion of subjects alive and free of respiratory failure (as defined above) at Day 14 Demonstration from baseling in CDD (time)
	• Percent change from baseline in CRP (time frame: baseline, Days 3, 5, 7, 10, 14, 28)
	• Change from baseline in ferritin (time frame: baseline, Days 3, 5, 7, 10, 14, 28)
	• Change from baseline in absolute lymphocyte counts (time frame: baseline, Days 3, 5, 7, 10, 14, 28)
	• All-cause mortality at Day 90
	• Proportion of subjects alive and discharged from the ICU at Days 14 and 28
	• Time from randomization to first occurrence of respiratory failure or death on study (up to 28 days after randomization) due to any cause
	• Number of days alive and free of respiratory failure from randomization to 28 days after randomization
	• Number of days with respiratory failure from randomization to 28 days after randomization
	• Number of days hospitalized from randomization to 28 days after randomization
	• Number of days in ICU (length of stay) from randomization to 90 days after randomization
	• Number of days alive outside of hospital from randomization to 28 days after randomization
	• Number of days alive outside of hospital from randomization to 90 days after randomization
	 Relative change from baseline in oxygenation index (SpO₂/FiO₂) to Days 3, 5, 7, and 10
	• Time to clinical improvement of at least 2 points (from randomization) on a 9-point

administered with BSC Exploratory Objectives	 points. PK parameters (eg, AUC and C_{max}) estimated, as appropriate. Exploratory Endpoints/Variables
To assess PK of acalabrutinib and its active metabolite in subjects with COVID-19 when	Summarized plasma concentrations of acalabrutinib and ACP-5862 at specified time
PK Objective	PK Endpoints/Variables
	• Time to $SpO_2 > 94\%$ on room air
	category ordinal scale through Day 28 (see Section 8.8.1)

AE = adverse event; AUC = area under the concentration-time curve; BSC = best supportive care; CL/F = apparent clearance; C_{max} = maximum observed concentration; COVID-19 = coronavirus disease 2019; CRP = C-reactive protein; FiO₂ = fraction of inspired oxygen; ICU = intensive care unit; CCI PK = pharmacokinetics; SAE = serious adverse event; SARS-CoV-2 = severe acute respiratory supdrama coronavirus 2; SpO₁ = oxygen saturation; to a = helf life; TEAE = treatment emergent adverse

syndrome coronavirus 2; SpO₂ = oxygen saturation; $t_{1/2}$ = half-life; TEAE = treatment-emergent adverse event; t_{max} = time to maximum observed concentration; CC Vd_{ss}/F = apparent volume of distribution at steady-state.

4. STUDY DESIGN

4.1 Overall Design

This is a multicenter, randomized, open-label, Phase 2 study that will evaluate acalabrutinib plus BSC versus BSC in subjects with COVID-19 who are hospitalized.

Subjects will be randomly assigned (1:1) to receive one of the following 2 treatments:

- Arm 1: Acalabrutinib 100 mg bid × 10 days + BSC (n=30)
- Arm 2: BSC alone (n=30)

For the purpose of this study, BSC is per discretion of the Investigator and institutional guidelines. However, refer to Section 5.2 and Section 6.5.3 for prohibited or restricted concomitant therapy. Subjects will be randomized based on the following stratification factors, which are considered prognostic factors for poor outcome:

- Age ($\geq 65 \text{ vs} < 65 \text{ years}$)
- Comorbidities (present vs absent). "Present" is defined as having at least 1 of the following comorbidities:
 - Cardiovascular disease, as defined by either heart failure New York Heart Association (NYHA) class ≥2 or hypertension requiring treatment
 - Diabetes mellitus requiring treatment
 - Chronic obstructive pulmonary disease or asthma requiring treatment
 - Current active solid tumor or hematologic malignancy

Inclusion/exclusion criteria are provided in Section 5. Assessments are provided in Section 1.1.

4.2 Scientific Rationale for Study Design

The immune system is required to clear viral infections and generate protective immunity from viral pathogens like SARS-CoV-2. There is significant evidence that in patients with severe respiratory problems, the immune system and inflammation contribute to the severity of the disease. Macrophages and neutrophils are key to producing cytokines driving this inflammation. The hypothesis being evaluated in this trial is whether Btk inhibition of the viral-induced macrophage and neutrophil immune response can decrease inflammation and reduce respiratory failure or death. Given the various covariates that contribute to these outcomes (eg, lack of consensus on standard of care, actively changing local treatment practices, and patients' comorbid conditions), a single-arm study will likely not be informative as data from historical controls are changing almost daily. Hence, this will be a randomized study. Subjects who are hospitalized for COVID-19 disease and meet the eligibility criteria will be randomized 1:1 to receive acalabrutinib plus BSC (n=30) versus BSC (n=30).

Stratification by age and comorbidities will be applied to randomization as these are expected to be important covariates.

4.3 Justification for Dose

Acalabrutinib 100 mg bid has been evaluated in various indications (ie, B-cell malignancies and solid tumours) alone and in combination with anti-CD20 antibodies, chemotherapy, a phosphatidylinositol-3-kinase (PI3K) inhibitor, and an anti-PD-1 antibody. No DLTs have been identified for acalabrutinib alone or when given in combination with these agents. For all of these indications, acalabrutinib was administered daily until disease progression; some subjects have been receiving acalabrutinib for > 5 years. The long-term safety experience of chronic administration of acalabrutinib 100 mg bid monotherapy and in combination with other agents, supports the proposed dosage of acalabrutinib is 100 mg bid for acute treatment. In addition, correlative studies—in subjects with chronic lymphocytic leukemia treated with acalabrutinib 200 mg once daily (qd) or 100 mg bid—show bid dosing maintained higher Btk

occupancy and achieved more potent NF-kappaB pathway inhibition compared with qd dosing (Sun et al 2020). Activation of NF-kappaB occurs in the lungs of patients with ARDS and may contribute to the increased expression of proinflammatory mediators (Moine et al 2000). Therefore, 100 mg bid dosing is proposed for this study to ensure maximum target engagement.

4.4 Internal DMC

This study will have an iDMC. Details of the roles and responsibilities of the iDMC and the safety and efficacy review will be provided in a separate iDMC charter. The iDMC will be responsible for reviewing the safety data periodically.

The iDMC will review the cumulative safety data approximately 28 days after the first 30 subjects (approximately 15 subjects per arm) are randomized.

In addition, if at any time during the conduct of the study either of the criteria below are met, enrollment of additional subjects will be paused such that the iDMC would convene and conduct a full safety review.

- Any death due to acalabrutinib (per Investigator)
- ≥20% treatment discontinuation rate due to toxicity attributed to acalabrutinib (per Investigator), when 10 or more acalabrutinib subjects have been treated
- Any Grade 4 hemorrhage due to acalabrutinib (per Investigator)

During the safety review, the iDMC with compare the known adverse event (AE) profile associated with acalabrutinib with comprehensive safety data from the current study. The iDMC will determine if an unacceptable increase in Grade 3 or higher AEs known to be associated with acalabrutinib occurred in the study. After the review, the iDMC will make a recommendation regarding study continuation, hold, or termination.

At the time of the safety review the iDMC will also review all available efficacy data and will support any health authority interactions or internal discussions based on their review. The study team will remain blinded to the data that the iDMC will review.

4.5 End of Study Definition

The end of study is defined as the last expected visit/contact of the last subject undergoing the study.

A subject is considered to have completed the study when he/she has completed his/her last scheduled procedure shown in the Schedule of Activities (SoA; Section 1.1). All randomized subjects will be followed for survival through 90 (\pm 7) days after randomization.

All subjects who discontinue the investigational study treatment for any reason other than withdrawal of consent, loss to follow-up, or death will have a safety follow up assessment 28 (\pm 3) days after the last dose of acalabrutinib (Arm 1), or 38 (\pm 3 days) after randomization for those subjects randomized to the BSC arm (Arm 2), as outlined in Section 1.1.

The study may be stopped if, in the judgment of the Sponsor, study subjects are placed at undue risk because of clinically significant findings.

See Appendix A 6 for guidelines for the dissemination of study results.

5. STUDY POPULATION

Prospective approval of protocol deviations to recruitment and enrollment criteria, also known as protocol waivers or exemptions, is not permitted.

Each subject should meet all the inclusion criteria and none of the exclusion criteria for this study to be assigned to a study intervention. Under no circumstances can there be exceptions to this rule. Subjects who do not meet the entry requirements are screen failures, refer to Section 5.3.

5.1 Inclusion Criteria

Subjects are eligible to be included in the study only if **all** of the criteria below apply.

- 1. Ability to understand the purpose and risks of the study and provide signed and dated informed consent or have a legal representative provide consent and authorization to use protected health information (in accordance with national and local patient privacy regulations).
- 2. Men and women ≥18 years of age at the time of signing the Informed Consent Form (ICF).
- 3. SARS-CoV-2 confirmed per World Health Organization criteria (including positive nucleic acid test of any specimen [eg, respiratory, blood, urine, stool, or other bodily fluid]) within 7 days of randomization.
- 4. COVID-19 pneumonia (documented radiographically) requiring hospitalization and oxygen saturation <94% on room air or requires supplemental oxygen.
- 5. Able to swallow pills.
- 6. Willing to follow contraception guidelines (refer to Appendix F).

5.2 Exclusion Criteria

Subjects are excluded from the study if **any** of the criteria below apply.

COVID-19 Related Medical Conditions

- 1. Respiratory failure at the time of screening (see Section 3 for definition of respiratory failure) due to COVID-19 pneumonia that impedes the ability to swallow pills, or in the opinion of the treating physician, the subject is likely to require mechanical ventilation within the immediate 24 hours and therefore unable to swallow pills.
- 2. Known medical resuscitation within 14 days of randomization.
- 3. Any serious medical condition or abnormality of clinical laboratory tests that, in the Investigator's judgment, precludes the subject's safe participation in and completion of the study.
- 4. Suspected uncontrolled active bacterial, fungal, viral, or other infection (besides infection with SARS-CoV-2).
- 5. In the opinion of the Investigator, progression to death is imminent and inevitable within the next 24 hours, irrespective of the provision of treatments.

Medical Conditions

- 6. Not expected to survive 28 days given their preexisting, uncorrectable medical condition, for example, subjects with, or suspected to have, the following conditions: multiorgan failure, poorly controlled neoplasms; endstage cardiac disease; cardiac arrest requiring cardiopulmonary resuscitation or with pulseless electrical activity or asystole within past 30 days; endstage lung disease; endstage liver disease; or human immunodeficiency virus (HIV)/acquired immunodeficiency syndrome with known endstage process.
- 7. Pregnant or breast feeding.
- 8. Alanine aminotransferase (ALT), aspartate aminotransferase (AST) and/or bilirubin $\geq 3 \times$ upper limit of normal (ULN) and/or severe hepatic impairment (Child-Pugh class C; see Appendix G) detected during the screening period (per local laboratory).

Exception: AST and/or ALT can be up to $5 \times$ ULN if considered due to underlying COVID-19 disease, but cannot be associated with concurrent elevated bilirubin (up to $2 \times$ ULN).

- 9. Absolute neutrophil count (ANC) $\leq 500/\mu$ L at screening (per local laboratory).
- 10. Platelet count $< 50,000/\mu$ L at screening (per local laboratory).
- 11. Estimated creatinine clearance of <30 mL/min calculated using the Cockcroft-Gault formula [(140age) × mass (kg)/(72 × creatinine mg/dL) multiply by 0.85 if female].
- 12. Uncontrolled or untreated symptomatic arrhythmias, myocardial infarction within the last 6 weeks, or congestive heart failure (NYHA Grade 3 or 4).

Exception: Subjects with controlled, asymptomatic atrial fibrillation during screening are allowed to enroll on study.

13. History of chronic hypercarbia, respiratory failure in past 6 months, or use of home oxygen in the setting of severe chronic respiratory disease.

- 14. Quadriplegia.
- 15. History of primary immunodeficiency, tuberculosis, progressive multifocal leukoencephalopathy (PML), aspergillus or other invasive mold/fungal infection, or received organ or bone marrow transplantation within 6 months of randomization.
- 16. Serology status reflecting active hepatitis B or C infection.
 - a) Subjects who are hepatitis B core antibody (anti-HBc) positive and who are hepatitis B surface antigen (HBsAg) negative will need to have a negative or undetectable hepatitis B viral load by quantitative polymerase chain reaction (PCR) result before randomization. Those who are HBsAg positive or have detectable hepatitis B viral load by PCR will be excluded.
 - b) Subjects who are hepatitis C virus (HCV) antibody positive will need to have a negative PCR result before randomization. Those who are hepatitis C PCR positive will be excluded.
- 17. Known active HIV with detectable viral load or CD4 counts < 500 cells/mm³.

Prior/Concomitant Therapy

- 18. Treatment with a strong cytochrome P450 (CYP)3A inhibitor (within 7 days before first dose of study drug) or inducer (within 14 days before first dose of study drug).
- Subjects are excluded who have already received prior immunomodulatory/ immunosuppressive treatment intended as specific treatment for COVID-19 (after randomization these agents may be permitted – see Section 6.5.2). Note: Steroids are permitted prior to randomization and on study..
- 20. Active participation in other drug clinical trials or received treatment with an investigational drug within 5 half-lives or 30 days (whichever is longer) of randomization/enrollment.

Exception: Subjects may receive COVID-19-specific antiviral drugs (eg, remdesivir, hydroxychloroquine).

- 21. Requires or is receiving specific anticoagulation with warfarin or equivalent vitamin K antagonists (eg, phenprocoumon) within 7 days prior to randomization. Other anticoagulants are permitted.
- 22. Subjects on dual antiplatelet **and** therapeutic anticoagulant therapy (eg, aspirin and therapeutic doses of low molecular weight heparin).
- 23. History of hypersensitivity (ie, allergic response) to active or inactive excipients of acalabrutinib or other Btk inhibitors.
- 24. Known cytoreductive chemotherapy treatment within 14 days of randomization.
- 25. Major surgery (as defined by the Investigator) within 4 weeks prior to randomization or still recovering from prior surgery.

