6.5.2 Permitted Concomitant Therapy

BSC for COVID-19 is required for all subjects in this study except as listed in Section 5.2 and Section 6.5.3. Given the rapid emergence of new data related to COVID-19, BSC could

change during the duration of the study. The use of therapies such as remdesivir, therapeutic plasma, corticosteroids, or other immunomodulatory agents (eg, tocilizumab) is permitted if recommended by local authorities and part of institutional policies or guidelines. The concomitant administration of immunosuppressive agents with acalabrutinib may require additional safety monitoring as determined by the treating clinician. Investigators should maintain prohibitions of certain concurrent medications for other reasons as listed in Section 6.5.3.

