6.5.3 Prohibited or Restricted Concomitant Therapy

The medications listed below are prohibited for all randomized subjects.

Medications Prohibited for All Subjects in Both Treatment Arms Through Day 28

Immunomodulatory drugs, intended as treatment for COVID-19 but not considered standard of care according to local institutional guidelines, are prohibited for all randomized subjects in the study through Day 28. Subjects who are taking immunomodulatory drugs for other medical conditions (eg, tocilizumab for rheumatoid arthritis) may continue with treatment upon discussion with the Medical Monitor.

Medications Prohibited for All Subjects in Both Treatment Arms Through Day 10

Strong CYP3A inhibitors or inducers: Drug-drug interactions may occur with some of the drugs being used as BSC (eg, drugs that are strong inducers or strong inhibitors of CYP3A). The concomitant use of strong inhibitors of CYP3A (see Appendix E) should be avoided by all subjects on the study. If a subject requires a strong CYP3A inhibitor while on treatment with acalabrutinib, discontinue acalabrutinib treatment. Conversely, concomitant administration of a strong inducer of CYP3A has the potential to decrease exposure of acalabrutinib and could reduce efficacy. Therefore, the concomitant use of strong CYP3A inducers should be avoided by all subjects in the study. If a subject requires a strong CYP3A inducer while on treatment with acalabrutinib, discontinue acalabrutinib. For additional information on drugs with potential drug-drug interactions, refer to Section 6.5.4.

Certain anticoagulants: Warfarin or equivalent vitamin K antagonists (eg, phenprocoumon) are prohibited for all subjects in the study. Subjects who require prophylaxis or therapeutic anticoagulation for thrombosis (deep vein thrombosis or pulmonary embolism) will be allowed to receive therapeutic anticoagulation with a non-vitamin K inhibitor class of anticoagulants (eg, heparin or low-molecular-weight heparin).

Refer to Section 5.2 for additional restrictions on concomitant therapy.

6.5.4 Acalabrutinib Drug-drug Interaction Guidance in the Presence of Life-threatening COVID-19 Infection

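### Exclusion 22 is ambiguous: its term points to two antiplatelet agents, but its only example has one, so some single-antiplatelet combinations could be enrolled

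*Protocol*

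**What the plan says.** Criterion 22 in Protocol Section 5.2 excludes "Subjects on dual antiplatelet" **and** therapeutic anticoagulant therapy; the *and* is bold in the protocol. The only illustration is "eg, aspirin and therapeutic doses of low molecular weight heparin". Criterion 21 excludes vitamin K antagonists and allows other anticoagulants. Section 5 says of the entry criteria: "Under no circumstances can there be exceptions to this rule".

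On study, the entry restrictions carry forward. Section 4.1 tells the reader to "refer to Section 5.2 and Section 6.5.3 for prohibited or restricted concomitant therapy". Section 6.5.2 requires best supportive care "except as listed in Section 5.2 and Section 6.5.3". Section 6.5.3 closes with "Refer to Section 5.2 for additional restrictions on concomitant therapy".

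Section 6.5.3 also gives an explicit action for one interaction: "If a subject requires a strong CYP3A inhibitor while on treatment with acalabrutinib, discontinue acalabrutinib treatment". There is a matching instruction for strong inducers. For thrombosis, it says subjects will be "allowed to receive therapeutic anticoagulation with a non-vitamin K inhibitor class of anticoagulants", and it does not mention antiplatelet agents.

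**The concern.** An eligibility rule has to be applied the same way at every site, and this one can be read in two ways. A clinician who takes *dual antiplatelet* in its usual sense looks for two antiplatelet agents plus a therapeutic anticoagulant. The example then fails the rule it is meant to illustrate, because aspirin is a single agent.

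What is at stake is bleeding safety. Section 6.6.1 reports haemorrhage, some of it fatal, in subjects treated with acalabrutinib. Table 5 gives major haemorrhage in 37 of 1040 subjects (3.6%) on monotherapy. Those were patients with haematologic malignancies on chronic dosing, so the figure shows a recognised risk and does not forecast the rate in a 10-day course for COVID-19.

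A misapplied criterion might also go unnoticed. Among the exclusion criteria, SAP Section 2.2 lists only criterion 1 as a key eligibility deviation.

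**Working it through.** No figure in the plan depends on this criterion, so there is nothing to recompute. The check is to apply each reading to the combinations a site could meet.

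- **Reading A:** *dual* qualifies *antiplatelet*. Exclusion needs two antiplatelet agents plus a therapeutic anticoagulant.
- **Reading B:** *dual* describes the pairing of two drug classes. Exclusion needs at least one antiplatelet agent plus a therapeutic anticoagulant.

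| Therapy at entry | Reading A | Reading B |
|---|---|---|
| Two antiplatelet agents + therapeutic anticoagulant | Excluded | Excluded |
| Aspirin + therapeutic LMWH (the printed example) | Not caught by the term, but named in the example | Excluded |
| A different single antiplatelet + therapeutic LMWH | Admitted | Excluded |
| Aspirin + another therapeutic anticoagulant that criterion 21 allows | Admitted | Excluded |
| One antiplatelet + an anticoagulant below therapeutic dose | Not covered | Not covered |

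The readings part only for subjects on exactly one antiplatelet agent plus a therapeutic anticoagulant. Within that group the printed pair is protected by name, so the real exposure is the third and fourth rows.

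Next, does any other current text settle the reading?

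1. **Definition.** Neither the protocol nor the SAP defines the term.
2. **Criterion 21.** It permits the relevant anticoagulants, which leaves criterion 22 as the only specific entry limit on combining them with an antiplatelet agent.
3. **Section 6.5.3.** It refers back to Section 5.2, so it inherits the ambiguity.
4. **Section 5.** It bars waivers. That rule does not decide what criterion 22 means.
5. **Amendment history (Appendix I, Amendment 2).** It describes the criterion with *combined* in place of *dual* and the same example. This is superseded text, and its difference from the current wording is not an error. It serves only as evidence that Reading B was intended.

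Finally, timing. SAP Section 1.3 records recruitment as complete with 62 randomized when version 3.0 was generated. Rewording the criterion could change the eligibility of none of those 62.

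**The case against.** The strongest reply is that the criterion explains itself. The word *therapy* follows both drug classes, the conjunction is bold, and the example fits Reading B exactly. A conflict arises only if a site chooses the reading that the example rules out. The rival reading also rests on general clinical usage, which the documents do not define. Most of this stands, and it is why the point is an ambiguity. What it does not remove is that the literal term and the example disagree, and a single example leaves the reader to work out which other pairs are covered.

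A second reply is that other safeguards exist:

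- the investigator's judgment (criterion 3) and the platelet cut-off (criterion 10);
- discontinuation after Grade 3 or 4, serious or intracranial haemorrhage (Section 6.7);
- discussion of immediate safety concerns with the Medical Monitor (Section 8);
- the enrolment pause for any Grade 4 haemorrhage due to acalabrutinib (Section 4.4).

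These limit the harm. None names this drug combination, and the discontinuation and pause rules act only after a bleed.

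A reader might also infer that the restriction lapses after randomization. The documents do not support that, because Sections 4.1, 6.5.2 and 6.5.3 all carry Section 5.2 into concomitant therapy. What Section 6.5.3 lacks is only a stated action of the kind it gives for CYP3A drugs. Asking for one is partly a matter of preference, so that part of the fix is optional.

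**Conclusion.** The point holds as a minor drafting ambiguity in a bleeding-safety exclusion. It assumes that some sites would give *dual antiplatelet* its usual two-agent meaning. The documents neither confirm nor exclude that.

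The impact is small. Eligibility is settled before randomization, so the comparison between arms is not affected, and no estimate, interval or power figure changes.

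A reader might be tempted to put a number on the subjects wrongly enrolled. The documents give neither the share of candidates on such combinations nor any sign of how sites read the rule. Applying an assumed share to all 62 randomized subjects would give at most a ceiling, because it presumes that every site used Reading A and enrolled every such candidate. No enrolment estimate is supported. With recruitment complete, the benefit lies in any further amendment or reuse of the text, and in clearer guidance for subjects still on treatment.

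**What to change.** In criterion 22, replace the operative words with: *Subjects on combined antiplatelet (one or more agents) and therapeutic anticoagulant therapy*, and keep the printed example. Rule and example then agree, and other single-antiplatelet pairs are plainly covered.

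Optionally, add one sentence to Section 6.5.3 on the CYP3A model: *If a subject requires combined antiplatelet and therapeutic anticoagulant therapy while on treatment with acalabrutinib, discontinue acalabrutinib.* The action should fall on acalabrutinib alone. An instruction to stop the antiplatelet agent during acalabrutinib dosing would change background care in one arm of an open-label trial, whereas the Section 6.5.3 prohibitions are written for both arms.

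The cost is one reworded line and, if adopted, one added sentence. A few more candidates would be excluded in any future use of the criterion, and a subject who needs both drug classes on study would lose the remaining acalabrutinib doses. That subject would still be analysed as randomized in the full analysis set.
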